## Study and Site Start and Closure

### First Act of Recruitment

- The study start date is the date when the clinical study will be open for recruitment.
- The first act of recruitment is when the site is opened and will be the study start date.

### Study Closure and Site Termination

- The Sponsor reserves the right to close the study site or terminate the study at any time and for any reason. Study sites will be closed upon study completion. A study site is considered closed when all required documents and study supplies have been collected and a site closure visit has been completed.
- The Investigator may initiate site closure at any time, provided there is reasonable cause and sufficient notice is given in advance of the intended termination.
- Reasons for the early closure of a study site by the Sponsor or Investigator may include:
  - Failure of the Investigator to comply with the protocol, the requirements of the IRB/IEC or local health authorities, the Sponsor's procedures, or GCP guidelines
  - Inadequate recruitment of participants by the Investigator
  - Discontinuation of further development of the Sponsor's compound
- If the study is prematurely terminated or suspended, the Sponsor will promptly inform the Investigators, the IECs/IRBs, the regulatory authorities, and any contract research organization(s) used in the study of the reason for termination or suspension, as specified by

the applicable regulatory requirements. The Investigator will promptly inform the participants and assure appropriate participant therapy and/or follow-up.

## Appendix 3 Contraception

### Definitions:

#### Woman of Childbearing Potential (WOCBP)

A woman is considered fertile following menarche and until becoming postmenopausal unless permanently sterile, as specified below.

If fertility is unclear (e.g., amenorrhea in adolescents or athletes) and a menstrual cycle cannot be confirmed before the first dose of study intervention, consider additional evaluation.

A WOCBP is **not**:

1. Premenarchal
2. A premenopausal female with 1 of the following:
  - Documented hysterectomy
  - Documented bilateral salpingectomy
  - Documented bilateral oophorectomy

Documentation can come from the site personnel's review of the female's medical records, medical examination, or medical history interview.

For a female with permanent infertility due to an alternate medical cause other than the above, (e.g., mullerian agenesis, androgen insensitivity), investigator discretion applies to determine study entry.

3. A postmenopausal female
  - A postmenopausal state is defined as no menses for 12 months without an alternative medical cause.
  - A high follicle-stimulating hormone (FSH) level in the postmenopausal range may be used to confirm a postmenopausal state in a female not using hormonal contraception or hormonal replacement therapy (HRT). However, in the absence of 12 months of amenorrhea, more than 1 FSH measurement is required in the postmenopausal range.
  - A female on HRT and whose menopausal status is in doubt will be required to use one of the non-estrogen hormonal highly effective contraception methods if she wishes to continue her HRT during the study. Otherwise, she must discontinue HRT to allow confirmation of postmenopausal status before study enrollment.

## Contraception Guidance:

| CONTRACEPTIVES ALLOWED DURING THE STUDY INCLUDE:   |
|---|
| Highly Effective Methods That Have Low User Dependency 

• Implantable progestogen-only hormone contraception associated with inhibition of ovulation

• Intrauterine device (IUD)

• Intrauterine hormone-releasing system (IUS)

• Bilateral tubal occlusion

• Vasectomized partner: a highly effective contraceptive method provided that the partner is the sole sexual partner of a WOCBP and the absence of sperm has been confirmed. Otherwise, use an additional highly effective method of contraception. The spermatogenesis cycle is approximately 90 days.

  |
| Highly Effective Methods That Are User Dependent 

• Combined (estrogen- and progestogen-containing) hormonal contraception associated with inhibition of ovulation

• Oral

• Intravaginal

• Transdermal

• Injectable

• Progestogen-only hormone contraception associated with inhibition of ovulation

• Oral

• Injectable

• Sexual abstinence: a highly effective method only if defined as refraining from intercourse during the entire period of risk associated with the study intervention. The reliability of sexual abstinence is evaluated in relation to the duration of the study.

  |
| Acceptable Methods 

• Progestogen-only oral hormonal contraception where inhibition of ovulation is not the primary mode of action

• Male or female condom with or without spermicide. Male condom and female condom cannot be used together (due to risk of failure with friction)

• Cervical cap, diaphragm, or sponge with spermicide

• A combination of male condom with either cervical cap, diaphragm, or sponge with spermicide (double-barrier methods)

   |
| 
Contraceptive use by men or women is consistent with local regulations regarding the use of contraceptive methods for those participating in clinical studies.
 
Highly effective methods have a failure rate of <1% per year when used consistently and correctly. Typical use failure rates differ from those when used consistently and correctly.
 
Hormonal contraception may be susceptible to interaction with the study intervention(s), which may reduce the efficacy of the contraceptive method. As such, male condoms must be used in addition to hormonal contraception. If locally required, in accordance with Clinical Trial Facilitation Group (CTFG) guidelines, acceptable contraceptive methods are limited to those which inhibit ovulation as the primary mode of action.
 
Acceptable methods are considered effective, but not highly effective (i.e., have a failure rate of <math>\geq 1\%</math> per year). Periodic abstinence (calendar, symptothermal, post-ovulation methods), withdrawal (coitus interruptus), spermicides only, and lactational amenorrhoea method (LAM) are not acceptable methods of contraception.
 |

## Appendix 4 Adverse Events: Definitions and Procedures for Recording, Evaluating, Follow-up, and Reporting

### AE Definition

| AE Definition   |
|---|
| 

An AE is any untoward medical occurrence in a patient or clinical study participant, temporally associated with the use of study intervention, whether considered related to the study intervention or not.

An AE can therefore be any unfavorable and unintended sign (including an abnormal laboratory finding), symptom, or disease (new or exacerbated) temporally associated with the use of study intervention. For surgical or diagnostic procedures, the condition/illness leading to such a procedure is considered as the AE rather than the procedure itself.

  |
| Events Meeting the AE Definition  |
| 

Any abnormal laboratory test results (hematology, clinical chemistry, or urinalysis) or other safety assessments (e.g., ECG, radiological scans, vital signs measurements), including those that worsen from baseline, considered clinically significant in the medical and scientific judgment of the Investigator (i.e., not related to progression of underlying disease).

Exacerbation of a chronic or intermittent pre-existing condition including either an increase in frequency and/or intensity of the condition.

New conditions detected or diagnosed after study intervention administration even though it may have been present before the start of the study.

Signs, symptoms, or the clinical sequelae of a suspected drug-drug interaction.

Signs, symptoms, or the clinical sequelae of a suspected overdose of either study intervention or a concomitant medication.

“Lack of efficacy” or “failure of expected pharmacological action” per se will not be reported as an AE or a SAE. However, the signs, symptoms, and/or clinical sequelae resulting from lack of efficacy will be reported as an AE or a SAE if they fulfil the definition of an AE or SAE.

 |
| Events NOT Meeting the AE Definition  |
| 

Unless judged by the Investigator to be more severe than expected for the participant’s condition, any clinically significant abnormal laboratory findings, other abnormal safety assessments that are associated with the underlying disease, the disease/disorder being studied, or expected progression, signs, or symptoms of the disease/disorder being studied.

Medical or surgical procedure (e.g., endoscopy, appendectomy): the condition that leads to the procedure is the AE.

Situations in which an untoward medical occurrence did not occur (social and/or convenience admission to a hospital).

   |

- Anticipated day-to-day fluctuations of pre-existing disease(s) or condition(s) present or detected at the start of the study that do not worsen.

## SAE Definition

If an event is not an AE per the definition above, then it cannot be an SAE even if serious conditions are met (e.g., hospitalization for signs/symptoms of the disease under study, death due to progression of disease).

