## 2.3.1 Risk assessment

| Identified and Potential Risks of Clinical Significance       | Summary of Data/Rationale for Risk   | Mitigation Strategy   |
|---|--|---|
| Study Intervention(s) [evobrutinib]                    |  |   |
| Identified risks:

Elevated liver transaminases. | 
Elevated liver transaminases have been observed in patients treated with evobrutinib across the program and is considered an important identified risk (for details see current IB). Elevations of liver transaminases were frequent, generally mild (Grade 1), asymptomatic and reversible, and occurred within 6 months of treatment. However, more severe cases were reported. This has not been observed in healthy participants after a single dose nor in patients within a week of treatment with evobrutinib.
 | 
As a single low dose of evobrutinib will be administered in this study, and given the short half-life of evobrutinib, worsening of liver function is unlikely to occur. Study participants will be confined, and liver tests will be monitored during the study.
                                   |
| Potential risks:

Embryo-fetal toxicity          | 
Based on nonclinical findings, embryo-fetal toxicity is considered as an important potential risk in participants exposed to evobrutinib.
   | 
Female participants of childbearing potential must not be pregnant, must have a negative pregnancy test at the time of enrollment and use highly effective contraception (Section 5.1) during the study period and for 120 days after the last dose and agree not to donate eggs for reproduction.
 |

| Identified and Potential Risks of Clinical Significance | Summary of Data/Rationale for Risk  | Mitigation Strategy   |
|---|---|---|
| Study Procedures                                 |   |   |
| Blood draw  | Blood draws have the potential to cause discomfort and adverse events such as fainting or hematoma. | Amount of blood drawn will be strictly controlled. Participants will be in a hospital setting with support from highly trained professionals.           |
| Electrocardiogram (ECG)                                 | Contact allergies can develop during ECG procedures.  | Participants with known contact allergies will not be included in the study. During ECG participants will be monitored by highly trained professionals. |
| Other  |   |   |
| Not applicable.   |   |   |

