### 8.2.4                    **Clinical Safety Laboratory Assessments**

Blood samples will be collected in a fasted condition (after a fast of at least 8 hours).

- Blood and urine samples will be collected for the clinical laboratory tests listed in [Appendix 5](#) at the time points listed in the SoA. All samples will be clearly identified.
- Additional tests may be performed at any time during the study, as determined necessary by the Investigator or required by local regulations.
- The tests will be performed by the local laboratory.
- The Sponsor will receive a list of the local laboratory normal ranges before shipment of study intervention(s). Any changes to the ranges during the study will be forwarded to the Sponsor or designated organization.
- The Investigator will review each laboratory report, document this review, and record any clinically relevant changes occurring during the study in the AE section of the CRF. The laboratory reports will be filed with the source documents.
- Additional serum or highly sensitive urine pregnancy tests may be conducted, as determined necessary by the investigator or required by local regulation, to establish the absence of pregnancy at any time during the study.

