**c. Requires inpatient hospitalization or prolongation of existing hospitalization**

- In general, hospitalization signifies that the participant has been detained (usually involving at least an overnight stay) at the hospital or emergency ward for observation and/or treatment that would not have been appropriate in the physician's office or outpatient setting. Complications that occur during hospitalization are AEs. If a complication prolongs hospitalization or fulfills any other serious criteria, the event is serious. When in doubt as to whether "hospitalization" occurred or was necessary, the AE will be considered serious.
- Hospitalization for elective treatment of a pre-existing condition that did not worsen from baseline is **not** considered an AE.
- However, all events leading to unplanned hospitalizations or unplanned prolongation of an elective hospitalization (i.e., undesirable effects of any administered treatment) must be documented and reported as SAEs.

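### Appendix 4 contradicts itself on whether liver-related worsening after dosing in Groups 2 and 3 is an AE or SAE

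*Protocol*

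**What the plan says.** Three pieces of Appendix 4 exclude disease-related events by default.

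- *Events Meeting the AE Definition* counts an abnormal laboratory result or other safety assessment as an AE if it is "considered clinically significant in the medical and scientific judgment of the Investigator (i.e., not related to progression of underlying disease".
- *Events NOT Meeting the AE Definition* excludes clinically significant laboratory findings and "other abnormal safety assessments that are associated with the underlying disease, the disease/disorder being studied, or expected progression, signs, or symptoms" of that disease. An exception opens the sentence: "Unless judged by the Investigator to be more severe than expected for the" participant's condition.
- *SAE Definition* adds: "If an event is not an AE per the definition above, then it cannot be an SAE even if serious conditions are met". Its examples are "hospitalization for signs/symptoms of the disease under study, death due to progression of disease".

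Other text includes such events.

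- *Events Meeting the AE Definition* also lists exacerbation of a pre-existing condition as an AE. The exclusion of day-to-day fluctuations applies only where the condition does not worsen.
- Protocol Section 8.2.4 tells the investigator to "record any clinically relevant changes occurring during the study in the AE section of the CRF".
- SAE criterion c requires "all events leading to unplanned hospitalizations or unplanned prolongation of an elective hospitalization" to be reported as SAEs, although a parenthesis describes these as undesirable effects of an administered treatment.
- *Assessment of Intensity* has the primary cause of any death reported as an SAE. SAP Section 15.2.1 likewise treats the cause of a death as the AE.

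On the drug, Section 2.3.1 states: "Elevated liver transaminases have been observed in patients treated with evobrutinib across the program and is considered an important identified risk". It is the only entry under identified risks.

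**The concern.** The exclusion reads like wording for an efficacy trial, where progression of the treated disease is an outcome and would otherwise flood the AE data. Here the disease being studied is cirrhosis with Child-Pugh class A or B impairment, and the drug's one identified risk appears in liver tests. Progression of the liver disease and an effect of the drug on the liver can look alike, so the rule reaches the same organ that the study has to watch.

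It also puts attribution ahead of recording. Appendix 4 defines an AE regardless of relatedness, and *Assessment of Causality* treats underlying disease as an alternative cause to be weighed and documented. Under the exclusion, the same judgment can remove an event before any causality assessment is made.

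Three things are at stake: the TEAE secondary endpoint, which SAP Section 15.1.1 summarizes by hepatic function group; the documented causality assessment; and SAE reporting within 24 hours under Section 8.3.1. The overtly healthy controls have no liver disease to which an event could be attributed, so any under-counting would run in one direction.

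**Working it through.** The plan gives no figure to reproduce. The check sets the rules side by side for a post-dose liver event in Group 2 or 3 that the investigator attributes to cirrhosis and considers within expectation.

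| Event | Text that excludes it | Text that includes it | Result |
|---|---|---|---|
| Worsening liver test | Underlying-disease exclusion; the progression qualifier on clinical significance | Section 8.2.4 | Tension: depends on whether clinically relevant is read with the same qualifier |
| Decompensation without admission | Underlying-disease exclusion | Exacerbation rule; fluctuations excluded only without worsening | Conflict |
| Unplanned admission for liver disease | First example under SAE Definition | Criterion c, limited by its parenthesis | Partial conflict: the parenthesis can be read as covering treatment effects only |
| Death from progression | Second example under SAE Definition | Assessment of Intensity; SAP Section 15.2.1 | Direct contradiction |

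Two careful investigators could classify the same event differently and each cite Appendix 4. Nothing in the appendix ranks the rules or says what counts as expected.

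**What other data would still show**

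- Liver tests are repeated on Day 2 and at Follow-Up (Section 1.3). They are listed with changes from baseline and flags, and summarized by time point, whatever their AE status (Section 9.4.2; SAP Section 15.3).
- Clinical decompensation is less well covered. Section 1.3 schedules ultrasound and encephalopathy assessment at Screening only, and the full physical examination at Screening and Day -1 only. After dosing, AE review is the main route by which new ascites or encephalopathy would enter the data.
- The final listings follow database lock (Section 9.4.4), so they cannot stand in for 24-hour reporting. The SAE listing in SAP Section 15.2.2 would carry forward any omission.

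**Scale**

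- Participants within reach of the exclusion: 8 mild + 8 moderate = 16.
- Total treated: 3 × 8 = 24, up to 24 + 4 = 28. Share: 16/28 = 57% to 16/24 = 67%.
- Controls: 8 to 12, none within reach of the liver-disease exclusion.
- One omitted participant with an event: 1/8 = 12.5 percentage points in one group, or 1/16 = 6.25 points across both impaired groups.

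These figures give the scale of a single omission. They do not estimate how often one would happen; the documents give no basis for that rate.

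**The case against.** The strongest reply is that the text keeps most of these events and that there is little occasion for the exclusion to apply.

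- An event judged worse than expected stays an AE, and decompensation fits the exacerbation rule. Criterion c also treats complications arising in hospital as AEs, and participants are confined from Day -1 until at least 32 hours after dosing.
- Impaired participants must have been clinically stable for at least 1 month before Screening (Section 5.1). Severe ascites and encephalopathy above Grade 1 are excluded (Section 5.2). Follow-Up falls on Day 4 to 6, so an investigator could hardly call decompensation in that window expected progression.
- Section 2.3.1 considers worsening of liver function unlikely after one low dose of a drug with a short half-life. It reports no transaminase elevations in healthy participants after a single dose, or in patients during their first week on the drug.
- Section 8 requires immediate safety concerns to be raised with the Sponsor at once, independently of SAE status.

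Most of this stands, and it makes an omission improbable. It does not settle which rule applies. The exception rests on unguided judgment in an open-label study. The single-dose experience comes from healthy participants and the first-week experience from patients; the exposed populations named in Section 2.3 do not include hepatic impairment, and Section 4.3 anticipates about 3-fold higher exposure in these groups. The duty in Section 8 does not decide SAE classification.

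A reader might go further and infer that Appendix 4 simply removes liver events in Groups 2 and 3, that worsening liver tests would be lost, or that criterion c makes every unplanned admission an SAE. The documents support none of these: the exception and the exacerbation rule retain events, laboratory values are reported regardless, and criterion c carries its parenthesis.

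**Conclusion.** The point holds as an internal contradiction in the AE and SAE definitions. It is clearest for death, where the second example under *SAE Definition* cannot be squared with *Assessment of Intensity*. It is weaker for admissions and laboratory changes, where the opposing text is qualified or leaves room for judgment.

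What can be lost is AE or SAE status, and with it the TEAE count, the causality assessment and 24-hour reporting. The events concerned are those attributed to cirrhosis and judged within expectation, in the 16 impaired participants. One such omission would shift a group's TEAE incidence by up to 12.5 percentage points, the full shift occurring if that participant had no other TEAE. TEAEs are summarized descriptively, so no hypothesis test is affected.

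The probability is low. A reader might picture further impaired participants being dosed without the Sponsor's knowledge, since Groups 2 and 3 are recruited in parallel and there is no special committee. Section 8 makes that less likely, and the documents do not establish it. The case for change is that stated rules conflict on the organ of the drug's only identified risk, and that reconciling them is cheap.

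**What to change.** Add one paragraph to Appendix 4 that reconciles the AE and SAE definitions with Section 8.2.4, criterion c and *Assessment of Intensity*. For hepatic events after dosing in Groups 2 and 3 it should state that:

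1. the underlying-disease exclusion, the progression qualifier on clinical significance and the two examples under *SAE Definition* do not apply;
2. clinically relevant worsening from the participant's own baseline is recorded as an AE;
3. seriousness is judged by SAE criteria a to f;
4. attribution to cirrhosis is handled under *Assessment of Causality*, after the event has been recorded.

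This changes a reporting definition only. It sets no laboratory threshold or clinical management rule, and the SAP's AE tables and listings can stay as they are. The cost is the paragraph itself and a few extra AE or SAE reports that may be judged unrelated.

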**A SAE is defined as any untoward medical occurrence that, at any dose:**

**a. Results in death**

**b. Is life-threatening**

The term 'life-threatening' in the definition of 'serious' refers to an event in which the participant was at risk of death at the time of the event. It does not refer to an event, which hypothetically might have caused death, if it were more severe.

**c. Requires inpatient hospitalization or prolongation of existing hospitalization**

- In general, hospitalization signifies that the participant has been detained (usually involving at least an overnight stay) at the hospital or emergency ward for observation and/or treatment that would not have been appropriate in the physician's office or outpatient setting. Complications that occur during hospitalization are AEs. If a complication prolongs hospitalization or fulfills any other serious criteria, the event is serious. When in doubt as to whether "hospitalization" occurred or was necessary, the AE will be considered serious.
- Hospitalization for elective treatment of a pre-existing condition that did not worsen from baseline is **not** considered an AE.
- However, all events leading to unplanned hospitalizations or unplanned prolongation of an elective hospitalization (i.e., undesirable effects of any administered treatment) must be documented and reported as SAEs.

